#### **4.10.11 Safety Monitoring**

##### **4.10.11.1 Data Review Committee**

A DRC (consisting of external rheumatology, infectious disease and respiratory experts, and GSK study team members that have no involvement in the acquisition of the data or direct contact with sites) will review ongoing unblinded safety data from the study and unblinded efficacy data at the interim analyses.

The first DRC review of safety data will be conducted after approximately 10 subjects per arm have completed 5 weeks of treatment, and subsequent reviews will take place approximately every 12 weeks thereafter until the end of the study.

Output shells for DRC outputs are provided in a separate document and the following outputs will be produced for each DRC review:

- Summary of Withdrawals by Reason for Withdrawal
- Summary of Demography Characteristics – Age, Gender and Weight
- Concomitant Medication
- Concomitant Medication of subjects with serious infections
- Concomitant Medication of subjects with DLCO Hemoglobin-corrected Percent of Predicted decrease  $>15\%$  change from baseline
- Summary of Treatment Emergent AEs - Overview
- Summary of Treatment Emergent AEs by SOC and PT
- Summary of AEs Leading to Withdrawal
- Plot of Most Common Adverse Events and Relative Risk
- Summary of SAEs
- Summary of AESIs of Serious Infections, Opportunistic Infections, Neutropenia, and PAP
- Summary of Hypersensitivity and Injection Site Reactions
- Summary of persistent cough, dyspnea or DLCO decrease
- Summary of Change from Baseline in DLCO Hemoglobin-corrected Percent of Predicted
- Summary of Proportion of Subjects with a  $>15\%$  Decrease from Baseline in DLCO Hemoglobin-corrected Percent of Predicted

- Summary Statistics of Haematology and Clinical Chemistry Values at Each Visit
- Distribution of Haemoglobin, Total WBCs, Neutrophil Counts, Platelet Counts, ALT, AST and Total Bilirubin by Visit and Treatment with Maximum over Time

For the interim efficacy analyses (when 90 subjects have completed 4 and 12 weeks of treatment) the time interval between subsequent reviews may deviate from the 12 weeks to combine these interim analyses with a safety review.

The decision to stop the study or randomisation to specific arms will be made by the DRC. Further details are given in the earlier sections of this RAP and will be included in the DRC Statistical Guidance document.

Unblinded efficacy data will also be reviewed if needed outside of the planned interim analyses to assess benefit/risk based on the safety findings. When possible, these reviews will be scheduled to align with planned safety reviews.

A vote of the DRC committee will be taken at the conclusion of each meeting of the DRC. Each meeting of the committee will be associated with an active recommendation of proceeding unchanged, modifying or terminating the study. Further details will be outlined in the DRC Charter.

#### **4.10.11.2 Medical Monitoring**

Medical monitoring will happen in form of monthly blinded data review meetings. Further details and the list of generated output can be found in the MDRP and the MMP.

#### **4.10.12 Immunogenicity**

Immunogenicity samples for determination of anti-drug-antibody (ADA) will be collected. Samples taken after dosing with GSK3196165 that have a value at or above the cut-point will be considered potentially treatment-emergent ADA-positive. Shift table from baseline to every assessment will be produced for the Immunogenicity population to assess the number of subjects going from:

- 1) negative → negative,
- 2) negative → positive,
- 3) positive → negative, and
- 4) positive → positive.

Serum analysis will be performed under the management of Immunogenicity and Clinical Immunology (ICI), GlaxoSmithKline. Serum will be tested for the presence of anti-GSK3196165 antibodies using the currently approved analytical methodology incorporating screening, confirmation and titration steps.

Anti-GSK3196165 Binding AB Detection (positive/negative) will be listed together with titre value (mL) and Rheumatoid Factor (positive/negative) for each subject with at least one positive result of Anti-GSK3196165 Binding AB Detection.

A Listing of DAS28 values will be produced for all subjects who developed ADA in the study, including rheumatoid factor and ADA status by visit.

## 4.11 Patient Reported Outcome (PRO) Measures

Change over time and change from baseline in RA Symptom and Impact Diary measures will be summarised for subjects that are in the ITT population but separately for subjects that are in the Actigraphy Population and subjects that are not in the Actigraphy Population. Responses for each of the 16 questions from the RA Symptom and Impact Diary will be summarised by visit. A repeated measures analysis of change from baseline in RA Symptom and Impact Diary measures will be done as done for DAS28(CRP) and other continuous efficacy parameters.

### 4.11.1 Actigraphy Substudy

During enrolment, subjects have the option to consent to participate in a substudy that collects data using an accelerometer in addition to the RA Symptom and Impact diary. The objective of the actigraphy substudy is to explore how actigraphy measurements of physical activity correlate to disease activity. [Table 9](#) lists the measures used to meet the protocol objectives.

**Table 9** Actigraphy Measures

Characteristic	Measures
Physical activity:	
 
• Percent time sedentary based on activity count cut-off*
 
• Percent time walking*
 
• Activity counts (i.e., total activity score)
 
• Average walking speed for durations of walking >1 min (m/s)
 
• Number of continuous walking periods from 2-10 min (w/ 1-30 second pause), 10-30 min (w/1-1 min pause), >30 min (w/1-1 min pause)
 

Morning stiffness:	
 
• Average sit-to-stand time during 1st 30 min after waking*
 
• Average lie-to-stand time during 1st 30 min after waking*
 
• Average activity counts for 2 hours after waking
 
• Average activity counts for 4 hours after waking
 

Sleep quality:	
 
• Percent time lying down during night-time
 
• Average number of nighttime movement episodes (per hour)
 
• Night-time rest efficiency defined as time NOT moving relative to time lying at night*
 
• Fragmentation indices (movement time (%) divided by the number of movement episodes during night-time rest, and average duration of movement episodes)*
 

RA Symptom and Impact Diary	
 
• 13 Symptom questions and 3 Impact questions
 

\* Measure is a change to or clarification of protocol wording.

#### 4.11.1.1 Accelerometer data collection

The accelerometer will be placed on the subject and returned to the site according to the Time and Events table in [Table 1](#). Results will be assigned to a visit as shown in [Table 10](#).

**Table 10** Accelerometer Placement and Removal

Day of Placement*	Day of Removal*	Visit
TP-GDO-WW-016-03 Effective Date: 26 Aug 15 Related to: SOP-GDO-WW-019	CONFIDENTIAL	Project Document Version No. 2.0 Project Document Effective Date: Date of last signature Page 65 of 80

Day -7	Day 7	Baseline = Day -7 to Day -1 Week 1 = Day 1 to Day 7
Day 71	Day 85	Week 12
Day 155	Day 169	Week 24
Day 239	Day 253	Week 36
Day 351	Day 365	Week 52
* Day of placement and removal are approximations.		

The raw accelerometer data will be analysed using an RA-specific algorithm developed by GSK and Imperial College London. At present, the algorithms are exploratory and not validated. A simple measure of overall activity level, “counts”, will be used as previously reported in the literature. Counts are a result of summing post-filtered accelerometer values into 1 minute epoch “chunks”, and represent a mapping from the raw acceleration for this specific fixed time period. Hence the value of the counts will vary based on the frequency and intensity of the raw acceleration. Measures determined in one minute epochs are collapsed into hourly and daily or 24-hour periods. The processed data will be reported according to whether the measure is collected during the daytime or night time hours, or over a 24-hour period:

- 24-hour period: The following measures will be reported within 24-hour periods starting at midnight and ending at 11:59:59 pm: average walking speed for walking bouts >1 minute, average activity counts per minute, number of continuous walking periods with duration 2-10 minutes, 10-30 minutes and >30 minutes, average sit-to-stand time and lie-to-stand time during 1st 30 minutes of getting up in the morning, average activity counts for the 2 hours and 4 hours after getting up.
- Night time: The following measures will be reported from the time of going to bed for the night until arising from bed in the morning: number of night time movement episodes per hour, night time rest efficiency, and fragmentation indices.
- Day time: The following measures will be reported from the time of getting out of bed in the morning until going to bed for the night: percent time sedentary, percent time walking, percent time lying down.

Each measure will be reported once per 24-hour period or day/night time unit of time to obtain up to approximately 7 days of data for baseline and Week 1, and up to approximately 14 days of data for Weeks 12, 24, 36, and 52.

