2. Evaluating treatment effects of GSK3196165 on physical activity and sleep in RA patients.
3. Evaluating how measures of physical activity relate to subject reported measures of symptoms and other efficacy assessments including DAS28(CRP), ACR and biomarkers of disease activity.

Measures to include but may not be limited to:

1. Daily and intra-daily physical activity to include time spent walking, time spent standing, time spent lying down, time spent sitting. Other measures may be derived from these data including overall time spent active, overall time spent sedentary, total Activity Score (amount and intensity of activity), duration of morning stiffness and number of continuous walking periods above a predefined threshold.
2. Sleep quality – to include time spent lying, number of movement episodes, sleep efficiency (function of % of movement time and % of lying time) and fragmentation index (function of movement time % and number of movement episodes).

The results from these assessments will be reported separately.

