

• Serum biomarkers which may be indicative of lung damage (e.g. KL-6, LDH, SP-D, cholestenic acid).

• Plasma biomarkers predictive of change in CYP3A4 activity.

• Baseline concentrations of GM-CSF autoantibodies.

• Immunogenicity.

Patient-Reported Outcomes

• Change over time and change from baseline in RA Symptom and Impact Diary measures.

• Change from baseline in BFI (Question 3) at Weeks 12, 24 and 52.

Actigraphy substudy at participating sites To explore how actigraphy measurements of physical activity correlate to disease activity, the following measures will be explored as change over time and change from baseline: 

• Inter- and intra-daily measures of physical activity including but not limited to:

◦ Time spent sedentary (sitting and lying), time spent active (walking and standing), total activity score (function of duration and intensity of activity), number and duration of continuous walking periods.

◦ Duration of morning stiffness.

• Measures of sleep quality including but not be limited to:

◦ Time lying, number of movement episodes, sleep efficiency (function of % of movement time and total % of lying time) and fragmentation index (function of movement time % and number of movement episodes).

• RA Symptom and Impact Diary.

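### SAP 4.11.1.1 puts percent time lying down, a night-time sleep measure in Table 9, in the daytime reporting window

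*SAP*

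**What the plan says.** SAP 4.11.1, Table 9 (Actigraphy Measures), sets out what the substudy will measure. Under sleep quality it has four entries, the first being "Percent time lying down during night-time".

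SAP 4.11.1.1 then assigns each processed measure to a 24-hour, night-time or day-time window:

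- The night-time window runs "from the time of going to bed for the night until arising from bed in the morning". Its list is "number of night time movement episodes per hour, night time rest efficiency, and fragmentation indices".
- The day-time window runs "from the time of getting out of bed in the morning until going to bed for the night". Its list is "percent time sedentary, percent time walking, percent time lying down".

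Elsewhere, time lying is a sleep measure. SAP section 2 begins its sleep-quality list with "Time lying, number of movement episodes, sleep efficiency", and Protocol 7.10.6 describes sleep quality as "to include time spent lying, number of movement episodes" and related measures. Protocol 7.10.6 also names lying among its daily activity measures: "time spent walking, time spent standing, time spent lying down, time spent sitting".

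**The concern.** One measure has two incompatible definitions in adjacent SAP sections. Table 9 says night; the processing rule says day. SAP 4.11.1.2 takes the median of each subject's daily values at each visit, forms the change from baseline in that median, and summarises it by actual treatment group. The reporting window therefore decides what is analysed.

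If the processing rule is programmed as written, a result presented as sleep quality would show how much the subject lay down while up for the day. That answers a different question. Two programmers could each follow the SAP and obtain different numbers.

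**Working it through.** No rate, power or sample size is involved, so the check sets the sections side by side.

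**1. The four sleep-quality entries in Table 9 and their windows in 4.11.1.1**

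| Table 9 sleep-quality entry | Window in 4.11.1.1 |
|---|---|
| Percent time lying down (night) | Day time |
| Night movement episodes per hour | Night time |
| Night-time rest efficiency | Night time |
| Fragmentation indices | Night time |

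Three of four agree; one conflicts.

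**2. Do the windows overlap?** The day window opens when the subject gets out of bed and closes at bedtime; the night window is its complement. However long the night is, none of it enters a value computed under the day-time rule. That value cannot be the Table 9 measure.

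**3. Could the daytime entry be an additional measure?** Count the accelerometer measures in each place.

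- Table 9: 5 physical activity + 4 morning stiffness + 4 sleep quality = 13.
- Section 4.11.1.1: 7 in the 24-hour list (walking speed, activity counts, walking periods, sit-to-stand time, lie-to-stand time, counts over 2 hours, counts over 4 hours) + 3 night + 3 day = 13.

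The two lists pair one to one, and lying down is the only pair whose windows conflict. If the daytime entry were a separate measure, it would be absent from Table 9 and the Table 9 night measure would have no reporting window.

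**4. Which window was intended?**

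- Time lying appears under sleep quality in Protocol section 3, Protocol 7.10.6 and SAP section 2.
- Table 9 marks changes to, or clarifications of, protocol wording with an asterisk; this entry has none.
- SAP 4.14, on changes to the planned analysis, mentions no move to daytime.

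These point to night-time. Only the phrase in 4.11.1.1 disagrees.

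**5. Does the error reach output?** Under 4.11.1.2 the measure receives univariate summaries of the median and of its change from baseline, plus boxplots of the change. With fewer than 30 substudy subjects, the boxplots give way to individual line plots of four other measures, but the summaries remain.

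**The case against.** The best counter-reading starts from Protocol 7.10.6, which also lists lying among the daily physical-activity measures. In 4.11.1.1 the phrase sits beside sedentary time and walking time, both activity measures. It might therefore be a deliberate daytime measure, with the real fault being an omission from the night-time list; moving the phrase would then delete something the protocol names. The one-to-one match of the 13 measures, and the lack of any daytime lying measure in Table 9, weigh against this. Even if it were right, the sections would still need reconciling.

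It is also fair that the error occurs only if 4.11.1.1 is followed. A programmer working from Table 9 would compute the intended measure, and neither section says which governs. The conclusion is conditional on that.

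The points about reach stand in full:

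- The substudy is exploratory, limited to consenting subjects at participating sites. Its algorithms are not validated, and its results come after the final analysis in a separate deliverable.
- Percent time lying down is not among the named line plots or scatter plots.
- Night-time rest efficiency has its own night-time denominator and is unaffected.
- Counting the two fragmentation indices separately makes the affected share one of five rather than one of four.

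**Conclusion.** The concern holds. Followed as written, SAP 4.11.1.1 computes one of the four Table 9 sleep-quality entries entirely from daytime data, and that entry then says nothing about sleep. This does not depend on any assumed length of night; it rests only on the two windows being disjoint and on 4.11.1.1 being the rule that is programmed. The other three sleep-quality entries, the diary questions on sleep, and all primary and secondary endpoints are unaffected. It is a minor correction, but it changes what is computed.

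**What to change.** In SAP 4.11.1.1, move percent time lying down from the day-time list to the night-time list, so that it matches Table 9. If daytime lying is also wanted, add it to Table 9 as a separate, named physical-activity measure with its own day-time window. It would help to state the denominator at the same time: within a window that runs from going to bed until getting up, the percentage could sit near 100% (an inference, since the algorithm is not described).

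The cost is one line in the SAP, with no new data collection. Make the change before the actigraphy programs are finalised, so that the window is not chosen after results have been seen.

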#### 4.11.1.2 Endpoint derivation and summaries

The median of the distribution of the daily values for each measure will be calculated for each subject and visit. Similarly, the median of the distribution of the daily responses for each of the questions in the RA Symptom and Impact diary will be calculated for each subject and visit. The endpoint for each measure (except for continuous walking periods) will be defined as the change from baseline for the median values, calculated as post-baseline median minus baseline median, where baseline is defined in [Table 10](#).

The median value and change from baseline in the median value for each actigraphy measure (excluding the number of continuous walking periods) and visit will be summarised with univariate statistics by actual treatment group, where visit data for subjects rescuing to the

highest dose will be grouped separately from the subjects randomised to that dose. Boxplots of the change from baseline in the median value will be plotted by actual treatment group. If less than 30 subjects participate in the Actigraphy substudy, then individual subject line plots will be produced for percent time sedentary, percent time walking, night-time rest efficiency and average counts/minute instead, using symbols to identify responses obtained at the rescue dose. Additional plots may be generated post hoc for other endpoints.

The number and percentage of continuous walking periods from 2-10 minutes, 10-30 minutes and >30 minutes will be summarised with categories 1, 2, 3, and  $\geq 4$  at each visit. The median response and change from baseline for the median response for each question from the RA Symptom and Impact diary questions will be summarised in a table. These data will not be graphed.

To assess the relationship between physical activity and DAS28(CRP), a scatter plot of activity counts versus DAS28(CRP) score over time will be provided using symbols to differentiate actual treatment group at each visit and a vertical bar where DAS28(CRP)=2.6 to identify responders from nonresponders. If there is sufficient data, a plot of change from baseline in activity counts versus change from baseline in DAS28(CRP) score over time and by DAS28(CRP) remission status will be provided instead of plots of the observed data using symbols to differentiate dose at each visit. Similarly, average walking speed versus DAS28(CRP) and night time rest efficiency versus DAS28(CRP) will be provided. The relationship between physical activity measures and ACR or biomarkers will not be investigated as stated in the protocol.

Plots will also be provided for the following efficacy endpoints versus questions from the RA Symptom and Impact diary by visit and by DAS28(CRP) remission status for all actigraphy subjects combined, using symbols to identify responses obtained at the rescue dose:

- Median percent time sedentary vs median Symptom Question 4 (worst pain while walking)
- Median activity counts vs median Symptom Question 8 (amount of energy)
- Median average sit-to-stand time vs median Symptom Question 1 (worst pain when sitting)
- Median average lie-to-stand time vs median Symptom Question 11 (early morning stiffness severity)
- Median night time rest efficiency vs median Symptom Question 2 (worst pain lying down)
- Median night time rest efficiency vs median Impact Question 2 (quality of sleep)
- Median functional index 1 (movement % / movement episodes) vs median Impact Question 3 (sleep affected by joint pain)
- Median functional index 2 (average duration of movement episodes) vs median Impact Question 3 (sleep affected by joint pain)

The results from these analyses will be reported after the Final analysis in a separate deliverable.

## 4.12 Other Analyses

### 4.12.1 Pharmacokinetic Analysis

A population PK model of GSK3196165 will be developed based on PK data from the current study as well as the 5 studies in healthy, RA and MS adult subjects (MSC1000, MOR103C104, MSC1001 and MOR103C103)

The main objectives of this analysis are as follows:

- To develop a population pharmacokinetic model that describes the single- and repeat-dose pharmacokinetics of GSK3196165 following intravenous (IV) and SC administration in healthy subjects and subjects with rheumatoid arthritis and multiple sclerosis;
- To identify covariates that may influence pharmacokinetics of GSK3196165;
- To derive post-hoc estimates of individual pharmacokinetic parameters characterising the PK time profile of GSK3196165 for any given dose

Further details on the population PK analysis are provided in a separate technical Analysis Plan (Population Pharmacokinetic Analysis of GSK3196165 Following Intravenous and Subcutaneous Administration to Healthy Volunteers, Subjects with Rheumatoid Arthritis and Multiple Sclerosis (Date: 08-Jan-2016)).

### 4.12.2 Pharmacokinetic / Pharmacodynamic (PK/PD) Exploratory Analysis

A graphical PK/PD exploration will be conducted to complement the statistical dose-response analysis and to visualize the nature of the concentration-response correlation. A variety of graphs will be generated per subject and in overall; where GSK3196165 concentration is characterised by the individual post-hoc estimates from the PK model, and the response is characterised by the individual values of the pharmacodynamic markers or efficacy (e.g. DAS28(CRP)) or safety endpoints (e.g. AE of special interest, lung damage biomarkers).

Example of PK/PD graphs:

- Linear scatterplot of change from baseline in CRP levels at week 12 versus steady-state average concentration values ( $C_{ave}$ ) estimated from the PK model
- Linear scatterplot of change from baseline in CRP levels at each visit versus pre-dose concentration values ( $C_{trough}$ ) at corresponding visit estimated from the PK model
- Linear scatterplot of change from baseline in DAS28(CRP) measures at week 12 versus  $C_{ave}$  estimated from the PK model
- Linear scatterplot of change from baseline in DAS28(CRP) measures at each visit versus  $C_{trough}$  at corresponding visit estimated from the PK model
- Boxplot of  $C_{ave}$  stratified by ACR20 at Week 12
- Boxplot of  $C_{ave}$  stratified by ACR50 at Week 12
- Boxplot of  $C_{ave}$  stratified by ACR70 at Week 12
- Boxplot of  $C_{ave}$  stratified by AE status

A separate PK/PD RAP will be created to define further detail of the PK/PD analysis.

